6.2 IMPORTANT PROTOCOL DEVIATIONS

CTP Section 7.3: *Important protocol deviation (iPD) categories will be suggested in the IQRM Plan. Important protocol deviations will be identified no later than in the Report Planning Meeting, and the IPD categories will be updated as needed.*

Consistency check listings (for identification of deviations from time windows) and a list of protocol deviations (e.g. deviations in drug administration, in blood sampling times, etc.) will be provided to be discussed at the Report Planning Meeting (RPM). At this meeting, it will be decided whether a discrepant data value can be used in the analyses or whether it must be corrected in the clinical database. Each protocol deviation must be assessed to determine whether it is an iPD. For the process of identification and managing iPDs refer to the BI reference document "Identify and Manage Important Protocol Deviations (iPD)" (2). For a

detailed specification of PDs and iPDs of this trial refer to the Integrated Quality and Risk Management Plan (IQRMP) Section 4.1.

If any iPDs are identified, they are to be summarised into categories and will be captured in the decision log. Categories which are considered to be iPDs in this trial are defined in the integrated quality and risk management plan (IQRMP). If the data show other iPDs, the definition in the IQRMP and the table below will be supplemented accordingly by the time of the RPM.

iPDs will be summarized and listed. Table 6.2: 1 below specifies which kind of iPDs could potentially lead to exclusion from which analysis set. The decision on exclusion of subjects from analysis sets will be made at the latest at the RPM, after discussion of exceptional cases and implications for analyses.

Table 6.2: 1 Handling of iPDs

iPD code	iPD Category & Brief Description	Excluded from which analysis set
A1	Inclusion Criteria Not Met	PKS
A2	Exclusion Criteria Met	PKS
B1	Informed consent not available/not done	TS, PKS
B2	Informed consent too late	None
C2	Randomisation not followed	PKS
C3	Non-compliance	PKS
C5	Incorrect intake of trial medication	PKS
C6	Improper washout between treatments	PKS
D1	Prohibited medication use	PKS
E1	Certain violations of procedures used to measure primary or secondary data	PKS
F1	Certain violations of time schedule used to measure primary or secondary data	PKS

6.3 SUBJECT SETS ANALYSED

Subject sets will be used as defined in the CTP, Section 7.3.

Table 6.3: 1 Subject sets analyzed

Class of endpoint	Subject set	
	TS	PKS
Disposition	X	
iPDs	X	
Primary PK endpoint		X
Further PK endpoints		X
Safety parameters & treatment exposure	X	
Demographic/baseline characteristics	X	

6.5 POOLING OF CENTRES

This section is not applicable, because the study was performed in only one centre.

6.6 HANDLING OF MISSING DATA AND OUTLIERS

Data of screened subjects who were withdrawn from the trial prior to first administration of any study drug will not be reported in the CTR.

Data of subjects who failed to complete all periods of the study (dropouts or withdrawals) will be reported in the CTR as far as their data are available. All withdrawals will be documented and the reason for withdrawal reported in the CTR.

CTP Section 7.5.1: *It is not planned to impute missing values for safety parameters.*

One exception where imputation might be necessary for safety evaluation are AE dates. Missing or incomplete AE dates are imputed according to BI standards (3).

Missing data and outliers of PK data are handled according to BI standards (4) and (5).

CTP Section 7.5.2: *PK parameters that cannot be reasonably calculated based on the available drug concentration-time data will not be imputed.*

6.7 BASELINE, TIME WINDOWS AND CALCULATED VISITS

A separate baseline is defined for each study treatment: Baseline is the last available value before administration of the respective formulation of BI 1265162.

Time windows are defined in Section 6.1 of the CTP. Adherence to time windows will be checked at the RPM.

7. PLANNED ANALYSIS

The format of the listings and tables will follow the BI guideline "Reporting of clinical trials and project summaries" (6).

The individual values of all subjects will be listed. Listings will be sorted by sequence group subject number and visit (if visit is applicable in the respective listing). AE listings will be sorted by assigned treatment (see [Section 7.8.1](#) below for details). The listings will be contained in Appendix 16.2 (SDL) of the CTR.

The following standard descriptive statistical parameters will be displayed in summary tables of continuous variables:

N	number of non-missing observations
Mean	arithmetic mean
SD	standard deviation
Min	minimum
Median	median
Max	maximum

For plasma concentrations as well as for all PK parameters the following descriptive statistics will additionally be calculated:

CV	arithmetic coefficient of variation
gMean	geometric mean
gCV	geometric coefficient of variation

For PK parameters the following descriptive statistics will additionally be calculated:

P10	10 th percentile
Q1	1 st quartile
Q3	3 rd quartile
P90	90 th percentile

The data format for descriptive statistics of plasma concentrations will be identical with the data format of the respective concentrations. The descriptive statistics of PK parameters will be calculated using the individual values with the number of decimal places as provided by the evaluation program. Then the individual values as well as the descriptive statistics will be reported with three significant digits in the CTR.

Tabulations of frequencies for categorical data will include all possible categories and will display the number of observations in a category as well as the percentage (%) relative to the respective treatment group. Percentages will be rounded to one decimal place. The category missing will be displayed if and only if there actually are missing values. Percentages will be based on all subjects in the respective subject set whether they have non-missing values or not.

7.1 DEMOGRAPHIC AND OTHER BASELINE CHARACTERISTICS

Only descriptive statistics are planned for this section of the CTR.

7.2 CONCOMITANT DISEASES AND MEDICATION

Concomitant diseases will be coded according to the most recent version of MedDRA. Concomitant medication will be coded according to the most recent version of the World Health Organisation – Drug Dictionary. Concomitant non-drug therapies will be coded according to the most recent version of MedDRA.

A medication will be considered concomitant, if it

- is ongoing at the time of first study drug administration, or
- starts within the analysis phase of the respective treatment (see [Section 6.1](#) for a definition of treatments and analysis phases).

The relevance of the concomitant therapies to the evaluation of PK will be decided no later than at the RPM.

Only descriptive statistics are planned for this section of the CTR.

7.3 TREATMENT COMPLIANCE

Treatment compliance will not be analyzed as a specific endpoint. Any deviations from complete intake will be addressed in the Report Planning Meeting (cf. [Section 6.2](#)) and described in the CTR.

7.4 PRIMARY ENDPOINT

7.4.1 Primary analysis of the primary endpoint

Primary analysis of the primary endpoint will be performed as defined in Section 7.3.1 of the CTP.

To assess the absolute bioavailability of the treatments, the statistical model for the primary analysis defined in the CTP is an analysis of variance (ANOVA) model on the logarithmic scale including "sequence", "period" and "treatment" as fixed effects and "subject within sequence" as random effect. Absolute bioavailability of the study treatments will be estimated by the ratios of the geometric means of (T1/R), (T2/R) and (T3/R) of the primary endpoint.

Exclusion of plasma concentrations

The ADS ADPC (PK concentrations per time-point or per time-interval) contains column variables ACEXC or ACEXCO indicating inclusion/exclusion (ACEXC) of a concentration and an analysis flag comment (ACEXCO). Exclusion of a concentration depends on the analysis flag comment ACEXCO. For example, if ACEXCO is set to "ALL CALC", the value will be excluded for all types of analyses based on concentrations. If ACEXCO is set to "DESC STATS" the value will be excluded from descriptive evaluations per planned time point/time interval. If ACEXCO contains the addition "TIME VIOLATION" or "TIME DEVIATION", the value can be used for further analyses based on actual times. If ACEXCO is set to "HALF LIFE", the value will be excluded from half-life calculation only; the value is included for all other analyses. Excluded concentration itself will be listed in the CTR associated with an appropriate flag.

Exclusion of PK parameters

The ADS ADPP contains column variables APEXC and APEXCO indicating inclusion/exclusion (APEXC) of a PK parameter and an analysis flag comment (APEXCO). All analyses based on the PKs are based on PK parameter values which are not flagged for exclusion, i.e. with APEXC equal to "Included".

Further details are given in "Noncompartmental Pharmacokinetic / Pharmacodynamic Analyses of Clinical Studies" (4) and "Description of Analytical Transfer Files and PK/PD Data Files" (5).

7.5 SECONDARY ENDPOINTS

7.5.1 Key secondary endpoints

This section is not applicable as no key secondary endpoint has been specified in the protocol.

7.5.2 Secondary endpoints

This section is not applicable as no secondary endpoint has been specified in the protocol.

7.7 EXTENT OF EXPOSURE

Descriptive statistics are planned for this section of the report.

7.8 SAFETY ANALYSIS

All safety analyses will be performed on the TS.

7.8.1 Adverse Events

AEs will be coded with the most recent version of MedDRA.

The analyses of AEs will be descriptive in nature. All analyses of AEs will be based on the number of subjects with AEs and not on the number of AEs.

For analysis, multiple AE occurrence data on the eCRF will be collapsed into one event provided that all of the following applies:

- All AE attributes are identical (lower level term, intensity, action taken, therapy required, seriousness, reason for seriousness, relationship, outcome, AESI)
- The occurrences were time-overlapping or time-adjacent (time-adjacency of two occurrences is given if the second occurrence started at most 1 hour after the first occurrence ended)

For further details on summarization of AE data, please refer to "Analysis and Presentation of Adverse Event Data from Clinical Trials" (7) and "Handling of missing and incomplete AE dates" (3).

The analysis of AEs will be based on the concept of treatment emergent AEs. That means that all AEs will be assigned to screening, on-treatment or follow-up phases as defined in [Section 6.1](#). AEs will be analysed based on actual treatments, as defined in [Table 6.1: 1](#).

An overall summary of AEs will be presented. This overall summary will comprise summary statistics for the class of other significant AEs according to ICH E3 (8) and for the class of AESIs.

CTP Section 5.2.6.2.2: *The following are considered as AESIs:*

- *Hepatic injury*
A hepatic injury is defined by the following alterations of hepatic laboratory parameters:
 - *An elevation of AST (aspartate transaminase) and/or ALT (alanine transaminase) ≥ 3 -fold ULN combined with an elevation of total bilirubin ≥ 2 -fold ULN measured in the same blood sample, or*
 - *Aminotransferase (ALT, and/or AST) elevations ≥ 10 fold ULN*

The investigator had to classify on the eCRF whether an observed AE was an AESI or not.

According to ICH E3 (8) AEs classified as "other significant" need to be reported and will include those non-serious and non-significant AEs

- (i) which are marked haematological or other lab abnormalities, or
- (ii) which were reported with "action taken = discontinuation" or "action taken = reduced", or
- (iii) which lead to significant concomitant therapy as identified by the Clinical Monitor/Investigator at a Medical Quality Review Meeting.

The frequency of subjects with AEs will be summarised by treatment, primary SOC and preferred term. AEs which were considered by the investigator to be drug related will be summarised separately. Separate tables will also be provided for subjects with SAEs, subjects with AESIs and subjects with other significant AEs (according to ICH E3 (8)). AEs will also be summarized by maximum intensity.

The SOC and preferred terms within SOC will be sorted by descending frequency over all treatment groups.

For disclosure of AE data on ClinicalTrials.gov, the frequency of subjects with non-serious AEs occurring with an incidence of greater than 5 % (in preferred terms) will be summarised by treatment, primary SOC and preferred term. The frequency of subjects with SAEs will also be summarised.

For disclosure of AE data in the EudraCT register, the frequency of AEs, the frequency of non-serious AEs with an incidence of greater than 5 % (in preferred terms) and the frequency of SAEs will be summarized.

For support of lay summaries, the frequency of subjects with drug-related SAEs will be summarized by treatment, primary SOC and preferred term.

7.8.2 Laboratory data

The analyses of laboratory data will be descriptive in nature and will be based on BI standards "Display and Analysis of Laboratory Data" (9).

Analyses will be based on normalised values, which means transforming to a standard unit and a standard reference range. The original values will be analysed if the transformation into standard unit is not possible for a parameter.

Descriptive statistics of laboratory values over time and for the difference from baseline (see [Section 6.7](#)) will be provided. Frequency tables of changes between baseline and last value on treatment with respect to the reference range will be presented.

Unscheduled measurements of laboratory data will be assumed to be repeat measurements of the most recent scheduled measurement (e.g. for follow-up or confirmation of a particular value). Therefore, unscheduled measurements will be assigned to the planned time point of the previous scheduled measurement. Descriptive statistics will be calculated by planned time point based on the worst value of the subject at that planned time point (or assigned to that planned time point).

Possibly clinically significant abnormal laboratory values are only those identified either in the Investigator's comments or at the RPM at the latest. It is the Investigator's responsibility to decide whether a lab value is clinically significant abnormal or not. Standard or project-

specific rules for flagging clinically significant values in an automated manner will not be applied in this study.

Clinically relevant findings in laboratory data will be reported as baseline conditions (prior to first administration of study treatment) or as AEs (after first administration of study treatment) if judged clinically relevant by the investigator, and will be analyzed as such.

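### The only reference-range frequency table described in the SAP uses the last on-treatment value, so an electrolyte shift seen at 2 h and resolved by then is counted as in range

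*SAP*

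**What the plan says.** SAP 7.8.2 sets out the laboratory summaries.

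- **Reference-range table.** "Frequency tables of changes between baseline and last value on treatment with respect to the reference range will be presented". The SAP text describes no other frequency table against the reference range.
- **Continuous summaries.** The SAP plans "Descriptive statistics of laboratory values over time and for the difference from baseline". For these, "Descriptive statistics will be calculated by planned time point based on the worst value of the subject at that planned time point". SAP section 7 lists the statistics shown: N, mean, SD, minimum, median and maximum.
- **Flagging.** The SAP states that "rules for flagging clinically significant values in an automated manner will not be applied in this study". Laboratory findings are reported "as AEs (after first administration of study treatment) if judged clinically relevant by the investigator".
- **Adverse event tables.** SAP 7.8.1 includes among other significant events those "which are marked haematological or other lab abnormalities", and "Separate tables will also be provided for subjects with SAEs, subjects with AESIs and subjects with other significant AEs".
- **Sponsor standard.** "The analyses of laboratory data will be descriptive in nature and will be based on BI standards"; the standard is reference 9 of the SAP and is not among the documents.

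Protocol 7.3.4 adds that out-of-range values are highlighted in the listings.

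The three protocol flow charts (oral, inhaled, intravenous) each mark a safety laboratory sample at 2 h, with a footnote limiting it to serum electrolytes, and one at 24 h without that limit. SAP Table 6.1: 1 sets the on-treatment phase at 48 h after administration, or less if the next dose or the end of participation comes first.

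**The concern.** Protocol 1.1 names a rise in serum potassium, or a fall in sodium or chloride, as the effect to expect from the mechanism if systemic exposure is excessive. The 2 h draw measures electrolytes and nothing else from the safety panel, and it is taken in all four treatments. The natural question for that sample is how many subjects crossed a reference limit after each treatment. The one table built to count crossings uses the last on-treatment value and so passes over the 2 h sample whenever a later one exists. A transient shift would then leave the table showing no change, although the sample that detected it was scheduled and taken.

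**Working it through.** The plan gives no figure to reproduce. The check has two parts.

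**1. Which sample is the last on-treatment value?**

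| Scheduled post-dose electrolytes | Hours after dose | Within 48 h? |
|---|---|---|
| Electrolytes only | 2 | yes |
| Full safety laboratory | 24 | yes |

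The last scheduled value is the one at 24 h. In period 4 the end-of-trial visit may fall on Day 3, about (3 − 1) × 24 = 48 h after dosing. If that sample falls inside the window it becomes the last value, and it too displaces the 2 h result. The 2 h value is used only when no later on-treatment value exists.

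A subject in range at baseline, out of range at 2 h and in range at the last value is therefore counted as in range before and after. A subject still out of range at the last value is counted as shifted. The worst-value rule does not change this, because it works within one planned time point and applies to the descriptive statistics.

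With 12 subjects and 4 treatments, complete data give:

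- 2 h results per electrolyte: 12 × 4 = 48
- 2 h and 24 h results per electrolyte: 12 × 4 × 2 = 96
- share not entering the table: 48/96 = 50%
- 2 h results for sodium, potassium and chloride together: 48 × 3 = 144

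**2. Do the planned 2 h statistics recover the count?**

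Take 12 subjects, one electrolyte and one treatment. Values are in steps of 0.1 relative to the upper limit: 0 is at the limit, and a positive value is above range. The lower limit is assumed to lie more than 1.0 below the upper, so no value falls below range.

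- Baseline, both sets: −1, −4, −8, −7, −5, −9, −5, −5, −5, −5, −4, −5 (all in range)
- Set A at 2 h: 0, 0, −10, 0, −2, −10, 0, 0, 3, −2, 0, 0
- Set B at 2 h: 1, 1, −10, −1, 1, −8, −5, 3, −2, −3, 1, 1
- Changes, A: 1, 4, −2, 7, 3, −1, 5, 5, 8, 3, 4, 5
- Changes, B: 2, 5, −2, 6, 6, 1, 0, 8, 3, 2, 5, 6

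The 2 h values have sum −21 and sum of squares 217 in both sets, so SD = √((217 − 21²/12)/11) = 4.048. The changes have sum 42 and sum of squares 244 in both sets, so SD = √((244 − 42²/12)/11) = 2.970. Dividing by 10:

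| | Mean | SD | Min | Median | Max |
|---|---|---|---|---|---|
| 2 h value, A and B | −0.175 | 0.405 | −1.0 | 0.0 | 0.3 |
| Change, A and B | 0.350 | 0.297 | −0.2 | 0.4 | 0.8 |

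Above range at 2 h: 1 of 12 (8.3%) in set A and 6 of 12 (50.0%) in set B. If all are back in range at 24 h, the last-value table shows 0 of 12 for both. The planned statistics therefore do not determine the count.

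**The case against.** The planned rule is clear and executable, and no document promises a count of 2 h shifts. The 2 h results are reported in several other ways: by time point, as change from baseline, in listings with out-of-range values highlighted, and as adverse events when judged clinically relevant. The 2 h minimum and maximum, on values normalised to a standard reference range, show whether any subject crossed a limit and by how far. With 12 subjects per treatment, the count can be read off the listing by hand. All of this stands, and it is why the point is minor.

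The example is also contrived. Seven of the 12 values in set A sit exactly at the limit, and five of the six exceedances in set B are only 0.1 above it. In both sets a reader would see a maximum above the limit. That is fair: the example shows that the count cannot be recovered from the summaries, and nothing about its likely size. Likewise, 50% is the share of results omitted by any last-value table with two post-dose times. It is not a share of shifts missed.

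Protocol 1.1 does not expect the effect with therapeutic inhalation, and Protocol 3.1 says low doses were chosen to keep concentrations in the range of the first-in-man trial. This lowers the stakes, but two of the four treatments are oral and intravenous, and the sample is taken in all of them.

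Finally, the sponsor standard and the ADS Plan mentioned in SAP 6.1 cannot be seen, and either may add a table by time point. That limits the finding to the SAP text.

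The objection does not supply the missing count. The adverse event route rests on judgement, because no automated rule flags clinically significant values, and the listing gives individual values without a frequency by treatment.

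**Conclusion.** The concern holds, at minor severity. As the SAP text stands, an electrolyte shift present at 2 h and resolved by the last on-treatment value is tabulated as in range, and no other described output counts such shifts by treatment. With complete data, 48 of 96 scheduled post-dose results per electrolyte do not enter the table. The documents give no time course for the electrolyte effect, so the number of shifts that would be hidden is unknown. The conclusion assumes that the 24 h sample is available and that the unseen sponsor standard does not already produce the table by time point. It affects only a descriptive safety summary; the bioavailability estimates and every decision rule are unchanged.

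**What to change.** In SAP 7.8.2, specify that for serum electrolytes the shift from baseline against the reference range is tabulated at each planned post-dose time point (2 h and 24 h) for each treatment. Keep the last on-treatment value for the other analytes. If reference 9 already produces this table, a sentence in 7.8.2 saying so is enough. The cost is one sentence and one extra descriptive table from data already collected.

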7.8.3 Vital signs

The analyses of vital signs (blood pressure and pulse rate) will be descriptive in nature. Descriptive statistics of vital signs over time and for the difference from baseline (see [Section 6.7](#)) will be provided.

Unscheduled measurements of vital signs will be assigned to planned time points in the same way as described above for laboratory data. However, for vital signs, descriptive statistics will be calculated by planned time point based on the last value of the subject at that planned time point (or assigned to that planned time point).

Clinically relevant findings in vital signs data will be reported as baseline conditions (prior to first administration of study treatment) or as AEs (after first administration of study treatment) if judged clinically relevant by the investigator, and will be analyzed as such.

7.8.4 ECG

Relevant ECG findings will be reported as relevant medical history/baseline condition (if a condition already exists before first administration of study treatment) or as AE (if condition emerges after first administration of study treatment) and will be summarized as such. No separate listing or analysis of ECG findings will be prepared.

